4.1 Inclusion Criteria

- Patient ≥ 18 years old
- Histologically confirmed diagnosis of melanoma
- Previously treated or previously untreated stage IV melanoma by AJCC staging criteria
- Presence of an index lesion between 1 and 5 cm
- ECOG Performance status 0, 1, or 2
- Signed informed consent document
- Adequate renal, hepatic, and hematologic indices for ipilimumab therapy
- Ability to tolerate stereotactic body radiation therapy (e.g. lie flat and hold position for treatment)

4.2 Exclusion Criteria

- Prior systemic therapy within 14 days of study enrollment. Patients must be adequately recovered from prior systemic therapy side effects as deemed by the treating investigator.
- Clinical contraindication to stereotactic body radiotherapy (e.g. active systemic sclerosis, active inflammatory bowel disease if bowel is within target field, etc)
- Presence of central nervous system metastasis (including active brain metastasis). Active brain metastasis would be defined as untreated brain metastases. If the brain metastases have received prior treatment (usually either with surgery or radiation), they are no longer active.
- Long-term use of systemic corticosteroids. Patients with replacement steroids and not immunosuppressive steroids may enroll in the study.
- Prior RT that precludes the delivery of SBRT

INCLUSION OF WOMEN AND MINORITIES

Female and male patients of all ethnic groups will be eligible for treatment in this protocol. Protocol accrual will be reviewed annually to include a determination of minority representation. An attempt will be made to enroll patients with metastatic melanoma in a distribution that matches the frequency of melanoma in the general population. The following melanoma incidence rates are reported by SEER: White 25.2 cases per 100,000; African-American 1.05 cases per 100,000; Asian/Pacific Islander 1.4 cases per 100,000; Hispanic 3.95 cases per 100,000.(26)

4.3 Subject Recruitment and Screening

Patients will be referred and screened by institutional standard practice. After the eligibility is established, a subject study number will be issued and the patient will be enrolled.

CONFIDENTIAL

This material is the property of the study sponsor. Do not disclose or use except as authorized in writing by the study sponsor

Printed on 1/31/2017

4.4 Early Withdrawal of Subjects

4.4.1 When and How to Withdraw Subjects

- Progressive Disease as determined by irRECIST 1.1 criteria.
- Extraordinary Medical Circumstances. If at any time the constraints of this protocol are detrimental to the subject's health, the subject will be removed from protocol therapy. In this event, the reasons for withdrawal will be documented.
- Subject's refusal to continue treatment. In this event, the reasons for withdrawal will be documented.

4.4.2 Data Collection and Follow-up for Withdrawn Subjects

Every effort will be made to follow subjects off study for toxicity, disease progression and survival.

5 Study Drug

5.1 Description

Ipilimumab is FDA approved for patients with metastatic melanoma and the delivery of this drug will be performed according to the FDA-approved dose and schedule. The Scientific Review Committee (SRC) has advised that an IND exemption is appropriate and will therefore be sought prior to initiation of this trial.

5.2 Dose Limiting Toxicities Definitions

Dose-limiting (Acute) Toxicity is defined as any treatment related Grade 4 or higher immune-related toxicity or Grade 3 or higher non-immune related toxicity which is observed during treatment or within 30 days of the final ipilimumab injection **and** which is probably or definitely related to radiation treatment. This definition will be used for de-escalation to the -1 dose level. All toxicities will be graded by NCI CTC Version 4.0.

Late toxicity Late toxicities will be graded according to the RTOG/EORTC late morbidity scoring system. The time frame for late toxicity is open-ended and late toxicities have been known to occur a year or more after therapy. Follow-up for late toxicity will cease when a patient experiences disease progression, since 2nd line therapies may then be initiated.

Non immune-related toxicity (SBRT-related toxicity) is defined as any toxicity observed within the tissues contained within the radiation portal and is consistent with tissue reaction to radiation exposure at any time during follow-up.

Immune-related toxicity is defined as an adverse event that is associated with exposure to ipilimumab and that is consistent with an immune phenomenon.

CONFIDENTIAL

This material is the property of the study sponsor. Do not disclose or use except as authorized in writing by the study sponsor

Printed on 1/31/2017

6 Study Procedures

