8.3 Endpoints

Toxicity: CTCAE version 4.0 grades will be employed. Any patient who receives any amount of radiotherapy or study medication will be included in the toxicity analysis.

Dose-limiting toxicity (DLT) is defined generally as associated with the treatment, and for ipilimumab, that the event must be consistent with an immune-related effect. DLT is experienced during study treatment or within 30 days after last injection of ipilimumab, as long as the patient has not started another systemic treatment for cancer and is defined more precisely in Section 5.2.

Maximum tolerated SBRT fraction (MTD) is defined as the SBRT fraction dose level at which 0-1/6 patients experience DLT and at least 2 patients treated at the next higher dose level experience DLT (or the apparent MTD is Dose level 1).

Late toxicity is defined generally as an adverse event associated with the treatment which occurs beyond 30 days after last injection (i.e., adverse events which are observed months after treatment are most likely associated with SBRT) and is defined more precisely in Section 5.2.

Response: Immune-related clinical response will be scored on a non-index lesion using immune-related response criteria (irRC) according to irRECIST 1.1 (48). Patients who do not complete a clinical response evaluation, with the exception of those patients with rapidly progressing disease, will be scored as unevaluable. The immune-related clinical response rate is defined as the proportion of patients treated at the MTD who achieve either a complete or partial immune-related response. Unevaluable patients are included in denominator for the calculation of the objective response rate.

Immunologic outcomes include: 1) analysis of lymphocyte subsets and lymphocyte activation, 2) analysis of antigen-specific T cells and 3) tumor-specific T cells, as described in Section 7.2.2. For T cell response analyses, overall immune response is defined as >2 fold pre-treatment/post-treatment increase in any of the key T cell parameters.

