8.4 Plans for De-escalation

A DLT rate $\geq 33\%$ is considered unacceptable. Enrollment will proceed independently in the two strata. If a DLT is observed, then all subsequent patients will be treated at Dose Level -1.

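### The two toxicity classes in Section 5.2 are not exhaustive, so a radiation-attributed Grade 3+ event that fits neither is left out of the automatic DLT count

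*Combined protocol and SAP*

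**What the plan says.** Section 5.2 sets the grade thresholds as "any treatment related Grade 4 or higher immune-related toxicity or Grade 3 or higher non-immune related toxicity". It adds a time window (during treatment, or within 30 days of the last ipilimumab injection) and an attribution condition: the event must be one "which is probably or definitely related to radiation treatment". On purpose it is explicit: "This definition will be used for de-escalation to the -1 dose level".

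The same section then defines the two classes. "Non immune-related toxicity (SBRT-related toxicity) is defined as any toxicity observed within the tissues contained within the radiation portal", with the further requirement that the event look like a tissue reaction to radiation. Immune-related toxicity is "an adverse event that is associated with exposure to ipilimumab and that is consistent with an immune phenomenon".

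Section 8.3 is looser. "Dose-limiting toxicity (DLT) is defined generally as associated with the treatment", with no grade and no reference to the portal. It then hands the detail back: "as long as the patient has not started another systemic treatment for cancer and is defined more precisely in Section 5.2".

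The count feeds two statements of the de-escalation rule. Section 8.4 says "If a DLT is observed, then all subsequent patients will be treated at Dose Level -1". Section 8.4.1 de-escalates after two or more DLTs at dose level 1, and says that DLTs at dose level -1 end the study.

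**The concern.** In ordinary speech, immune-related and non-immune-related cover everything between them. As Section 5.2 defines them, they do not. The non-immune class is narrowed to in-portal tissue reactions, and nothing takes up what remains. An investigator could judge a Grade 3, 4 or 5 event to be definitely due to the radiation and still find no limb of the DLT definition that covers it.

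What is at stake is the automatic part of the safety rule. The rule acts on very few events, so leaving one out can decide whether later patients in that stratum stay on three fractions. There is also a consistency problem. One investigator might apply the printed definition and another the everyday meaning of non-immune, and they would classify the same event differently.

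**Working it through.** This is a check of definitions. No stated figure is in dispute.

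**Step 1: the plan's own figure.** The operating characteristics in 8.4.2 are the only figures in the plan that rest on a DLT count. They are the binomial probability of 0 or 1 DLT in 6 patients. At a true rate of 40%:

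0.6^6 + 6 × 0.4 × 0.6^5 = 0.0467 + 0.1866 = 0.233, against the stated 0.23.

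The other columns reproduce as well. The table takes the DLT rate as given and does not address which events count as DLTs, so it neither reveals nor closes the gap.

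**Step 2: apply the definitions.** Take an event inside the time window that is judged probably or definitely related to radiation. Ask two questions: does it meet the immune-related definition, and is it an in-portal tissue reaction?

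| Immune-related definition met | In-portal tissue reaction | DLT threshold under 5.2 |
|---|---|---|
| No | Yes | Grade 3 |
| Yes | No | Grade 4 |
| Yes | Yes | Grade 3 (either limb suffices, because they are joined by or) |
| No | No | None |

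The last row is the gap. The third row is already settled by the literal wording.

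**Step 3: look for a catch-all elsewhere.**
- Section 8.3 has the broader general wording, but it states no grade and defers to 5.2.
- Section 8.4.3 monitors late events using the same two classes and refers back to 5.2.
- Sections 8.4 and 8.4.1 use the term DLT without redefining it.

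None of these gives the last row a threshold.

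**Step 4: consequence for the rule.** De-escalation needs 1 DLT under 8.4 and 2 under 8.4.1. That conflict is a separate matter. Here it only shows how small the deciding count is. Under 8.4 an uncounted event matters if it would have been the first. Under 8.4.1 it matters if it would have brought the count to two.

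**Step 5: what cannot be computed.** The documents do not say what share of radiation-attributed events falls in the last row. Any change in the 0.23 would need an invented share, so none is given.

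**The case against.** The strongest reply is that the uncovered set is nearly empty. Radiation goes to a single lesion of 1 to 5 cm, and the protocol labels in-portal reactions as SBRT-related toxicity. An event that is Grade 3 or higher, confidently attributed to radiation, not an in-portal tissue reaction and without immune features would be unusual. Limiting radiation DLTs to in-field effects is also a recognisable attribution choice. Much of this stands, and it is why the point is small. It does not remove the gap. The broader wording in 8.3 suggests the exclusion was not intended, and a safety rule should not depend on readers setting aside its own definition.

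A reader might infer that such an event could not lead to de-escalation at all, or would go unnoticed. The documents do not support that. Section 8.1 separately reduces the dose in a stratum if three fractions prove unsafe, without tying this to a DLT count. Section 10.2 makes committee approval a condition of continuing. Section 8.5 analyses toxicity in every patient who receives any radiation or study medication, Section 9.2 has adverse events assessed for severity and relatedness, and Section 9.3 has serious ones reported.

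A reader might also infer that local injury just beyond the target falls in the gap, because Table 1 permits appreciable dose 2 cm from the planning target volume (PTV). That works only if portal means the PTV. The protocol defines PTV separately and uses a different word here. Section 6.2.4 describes multiple beams with apertures shaped to the PTV's projection, so tissue along the beams is more naturally inside the portal. The dose limits are also planning ceilings and say nothing about how often toxicity occurs.

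**Conclusion.** The point holds in a limited form. On the printed definitions, an acute Grade 3 or higher toxicity probably or definitely related to radiation is not a DLT if it has no immune features and is either outside the portal or not a typical tissue reaction. It therefore does not count toward the rule in 8.4 and 8.4.1. What is lost is the automatic count. Discretionary routes to action remain.

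The size is one event at a time, set against a threshold of one or two. Such events are probably uncommon; that is a judgement, since the documents give no frequency. No effect on the DLT rate or the operating characteristics is claimed, and no dose figure supports the point. The conclusion assumes that the definitions in 5.2 are applied as written, as 8.3 directs. This is a cheap improvement to a safety definition and does not undermine the design.

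**What to change.** In 5.2, mirrored in 8.3, define non-immune-related toxicity in two limbs: any toxicity within the irradiated tissues that is consistent with a radiation reaction, or any other toxicity that does not meet the immune-related definition. Grade 3 then becomes the default threshold and every radiation-attributed event has one.

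Keep the time window, the attribution condition, and the Grade 4 threshold for events that are only immune-related. An event meeting both definitions stays at Grade 3, as the present wording implies. The SBRT-related label is best left on the first limb, because 8.4.3 uses it for late toxicity.

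The cost is about one sentence in each section. The DLT count may rise slightly, and because DLTs at dose level -1 end the study, a newly counted event could contribute to termination. The requirement that the event be probably or definitely related to radiation limits that risk.

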9.2.2 Adverse Event Causality

The Investigator will use the following definitions to assess the relationship of the adverse event to the use of study treatment:

Related - An adverse event has a strong temporal relationship to study drug, recurs on rechallenge or is known to be an effect of the study drug. Another reasonable etiology either doesn't exist or is unlikely.

CONFIDENTIAL

This material is the property of the study sponsor. Do not disclose or use except as authorized in writing by the study sponsor

Printed on 1/31/2017

Possibly Related - An adverse event has a strong temporal relationship to the study drug and an alternative etiology is either equally or less likely when compared to the potential relationship to study drug.

Not Related - An adverse event is due to an underlying or concurrent illness or effect of another drug and is not related to the study drug (e.g., has little or no temporal relationship to study drug or has a much more likely alternative etiology).

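### The DLT trigger needs a probable or definite relation to radiation, but the protocol's only causality scale has neither those levels nor a radiation attribution

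*Combined protocol and SAP*

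**What the plan says.** Section 5.2 sets grade thresholds for a DLT (Grade 4 or higher if immune-related, Grade 3 or higher otherwise) and a time window. It then adds a causal condition: the event must be one "which is probably or definitely related to radiation treatment". It also fixes the purpose: "This definition will be used for de-escalation to the -1 dose level". The same section states what immune-related means: "Immune-related toxicity is defined as an adverse event that is associated with exposure to ipilimumab". Non-immune toxicity is described there as a reaction inside the radiation portal that is consistent with radiation exposure.

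Section 9.2.2 is the only place where causality levels are defined. Its lead-in says the investigator uses them "to assess the relationship of the adverse event to the use of study treatment". The three levels begin:

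- "Related - An adverse event has a strong temporal relationship to study drug, recurs on rechallenge"
- "Possibly Related - An adverse event has a strong temporal relationship to the study drug"
- "Not Related - An adverse event is due to an underlying or concurrent illness or effect of another drug"

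Section 8.3 gives a general description: "Dose-limiting toxicity (DLT) is defined generally as associated with the treatment, and for ipilimumab, that the event must be consistent with an immune-related effect". It refers to Section 5.2 for the precise definition, and it stops counting once the patient starts another systemic cancer treatment. Section 8.5 plans to describe attribution to SBRT or to ipilimumab only where possible.

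**The concern.** The trial's dose decision rests on a small count of DLTs. Sections 6.2.3 and 8.4 move to Dose Level -1 after one DLT, Section 8.4.1 after two or more, and Section 8.4.1 ends the study if DLTs occur at Dose Level -1. Whether an event enters that count depends on a graded judgement about radiation. The protocol's causality scale uses other labels and is worded against a different agent. Two investigators could classify the same event differently and both cite the protocol, and a committee reviewing the stopping rules under Section 10.2 could not resolve the matter from causality recorded under Section 9.2.2.

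**Working it through.** **1. The plan's own figure.** The only stated figures that depend on how DLTs are counted are the operating characteristics in Section 8.4.2. They follow from 0 or 1 DLT in 6 patients:

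P(X ≤ 1) = (1−p)^6 + 6p(1−p)^5

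At p = 0.40 this is 0.0467 + 0.1866 = 0.233, against 0.23 stated. The other columns also reproduce (0.886, 0.655, 0.420, 0.109, 0.041, 0.011, 0.0016 and 0.00006 at 10%, 20%, 30%, 50%, 60%, 70%, 80% and 90%). The table is arithmetically correct, but it presupposes that each event can be classed as a DLT or not. To show the sensitivity, assume that only half of the treatment-associated events of DLT grade pass the radiation condition. A true 40% rate then behaves like the 20% column, and 0.23 becomes 0.66. The half is my assumption; the documents give no such fraction.

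**2. The rule set beside the scale.**

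| | Section 5.2 (trigger) | Section 9.2.2 (scale) |
|---|---|---|
| Agent judged | Radiation | Study treatment in the lead-in; study drug in all three levels |
| Levels | Probably, definitely | Related, Possibly Related, Not Related |

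- *Agent.* Section 5 is headed Study Drug and describes only ipilimumab. No level in Section 9.2.2 is worded for radiation.
- *Labels.* Possibly Related covers an alternative cause that is equally likely or less likely than the drug. It therefore runs from an even balance to cases that many would call probable, and the boundary that Section 5.2 needs falls inside one level.
- *Direction.* Not Related includes events with a much more likely cause other than the drug. Read literally, a clear radiation injury fits, so an event that plainly meets Section 5.2 could be recorded as Not Related.
- *Other text.* Section 10.5 mentions possibly or probably related events, but only for IRB notification, again against the study drug and without defining levels.

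**3. The two arms of Section 5.2.** The non-immune arm has a partial test of its own (location in the portal and type of tissue reaction). The immune-related arm has none. It requires association with ipilimumab and also a probable or definite relation to radiation, with no scale for that double judgement.

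**4. Illustration of what depends on the immune-related arm.** Section 1.1 gives only a combined Grade 3 or 4 immune-related rate of 10 to 15% on ipilimumab. Assume a Grade 4 rate p of 2%, 5% or 8%. Take n = 20 per stratum (Section 8.1), and suppose such events count.

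P(≥1) = 1 − (1−p)^20

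P(≥2) = 1 − (1−p)^20 − 20p(1−p)^19

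| Assumed p | (1−p)^20 | 20p(1−p)^19 | P(≥2) | P(≥1) |
|---|---|---|---|---|
| 2% | 0.668 | 0.272 | 0.06 | 0.33 |
| 5% | 0.358 | 0.377 | 0.26 | 0.64 |
| 8% | 0.189 | 0.328 | 0.48 | 0.81 |

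Both columns are needed because Sections 6.2.3 and 8.4 state a one-DLT trigger and Section 8.4.1 a two-DLT trigger. The top value is high relative to the source: 8% is 53% of 15% and 80% of 10%.

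**The case against.** The other side has several good points.

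- **Section 8.3 is not a rival definition.** A reader might infer that the same Grade 4 immune-related event is a DLT under Section 8.3 and not under Section 5.2. The documents do not support that. Section 8.3 calls itself general, sets no grade threshold and defers to Section 5.2. What remains is smaller: its cut-off at another systemic cancer treatment is absent from Section 5.2.
- **The data may be collected.** A reader might infer that radiation attribution is never recorded. The adverse event form is not in the documents, and Section 8.5 contemplates attribution to either agent. The supportable statement is that the protocol defines no radiation causality scale.
- **Section 5.2 is not wholly unusable.** The non-immune arm has its own radiation test, and an investigator could judge probable or definite relation directly. That stands, but it leaves an undefined judgement in control of de-escalation and termination.
- **Double attribution may be intended.** The rationale in Section 1.1 is that SBRT starts an immune response which ipilimumab then extends, and only SBRT is de-escalated. A trigger limited to radiation-related events may therefore be deliberate. Equally, nothing in the documents shows that few immune-related events would meet the condition, or that the chance of reaching the trigger would then be near zero. Neither should be inferred.

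None of this removes the mismatch of labels and agent between Sections 5.2 and 9.2.2.

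**Conclusion.** The point holds as a conflict within the safety trigger. Causality recorded under Section 9.2.2 cannot show whether the Section 5.2 condition is met, and for a radiation injury it could point the wrong way. The ambiguity is greatest for immune-related events and partial for non-immune events. The missing systemic-treatment cut-off in Section 5.2 is a secondary inconsistency.

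This conclusion rests on the text and needs no numerical assumption. The probabilities of 6% to 48% (two-DLT trigger) and 33% to 81% (one-DLT trigger) are illustrations only. They assume the Grade 4 rates, a full stratum of 20 treated and observed at the starting level, independent patients, and that all such events count. They do not estimate the difference between two definitions, because the share of these events that would be attributed to radiation is unknown.

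**What to change.** Reconcile Sections 5.2, 8.3 and 9.2.2 into one DLT definition and one set of causality labels. State in that definition whether the cut-off at another systemic cancer treatment applies. Record attribution to SBRT and attribution to ipilimumab separately for every adverse event, using those labels, so that the DLT count can be read from the data. The investigators must decide which events count, including how an immune-related event attributed to both agents is handled. The one-DLT and two-DLT wordings in Sections 6.2.3, 8.4 and 8.4.1 must also be reconciled, since the count cannot be acted on consistently otherwise.

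Cost: protocol wording, plus two attribution items on the adverse event form if it does not already have them.

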Stereotactic body radiotherapy (SBRT) is a highly precise treatment technique that delivers large tumoricidal doses of radiation to a small tumor. Although this represents one of the most exciting and active frontiers of research in the radiotherapeutic management of early stage NSCLC, this treatment technique was originally developed in 1951 by a Swedish neurosurgeon, Lars Leksell for the treatment of intracranial metastases.(5) SBRT allows for escalation of dose without extending the overall treatment duration, as would be the case with conventional fractionated radiotherapy. A Phase I dose-escalation trial evaluated patients with T1-2 N0 NSCLC with no restriction on tumor location. Each treatment course was administered over 3 fractions with a starting dose of 8 Gy per fraction. Patients were stratified into 3 dose-escalation groups based on T stage and size (T1, T2 <5 cm, and T2 5–7 cm). This trial demonstrated that the maximally tolerated dose for T2 tumors larger than 5 cm was 22 Gy × 3 for, and was not reached at 20 Gy × 3 for T1 tumors or at 22 Gy × 3 for T2 tumors smaller than 5 cm.(6). There were a total of 10 local failures in the 47 patients treated in this study with nine local failures in patients treated to the lower dose levels (<16Gy x 3). A Phase II trial from the same group of investigators treated 70 patients with Stage I NSCLC with the doses established in the phase I study. With a median follow-up of 17.5 months, the local control was 95%, which appears at least as effective as a definitive surgical resection. Severe toxicity occurred at a median of 10.5 months in 17% of those patients with peripheral lesions versus 46% with central lesions.(7) Several other institutions have subsequently published their experience utilizing SBRT for early lung cancer with a variety of dose fractionation and prescription schemes. The initial data appear promising with 80%–100% local control, 40%–100% 2- to 3-year survival, and 0%–4% grade 3 toxicity), although in general the median follow-up for these studies is relatively short.(8-14). Given these promising results, the RTOG (RTOG 0618) has initiated a phase II study of stereotactic body radiotherapy for operable patients with early stage operable NSCLC. Additionally, [name] initiated a randomized trial of surgical resection vs. stereotactic body radiation for early stage lung cancer in early 2010 (RTOG 1021). While the results of these studies are eagerly anticipated, the ability to treat early stage lung cancer with SBRT is rapidly being incorporated into most Radiation Oncology facilities here in the United States.

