3.1 General Design

This is a stratified phase II study of escalating fractions of stereotactic body radiotherapy (SBRT) combined with immunotherapy for previously untreated or previously treated metastatic melanoma patients. Patients will undergo a short course of high dose SBRT to a single index lesion that measures 1 cm to 5 cm. These fractions will be administered several days apart. Radiotherapy will be immediately followed by ipilimumab, at the FDA-approved dose and schedule.

RADVAX TRIAL

Study Duration: The expected accrual rate = 15 pts/yr. The protocol is designed for a maximum total of 40 patients. The expected total study duration is 3 to 3 ½ yrs needed to complete both phases, allowing for suspensions for interim analyses.

*Study Enrollment is intended to mean consultation

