8.5 Plans for Data Analysis

Toxicity: Any patient who receives any amount of radiation or study medication will be analyzed for toxicity. All dose-limiting toxicities and late toxicities will be graded and tabled by lesion site

CONFIDENTIAL

This material is the property of the study sponsor. Do not disclose or use except as authorized in writing by the study sponsor

Printed on 1/31/2017

stratum and SBRT fraction dose level. Toxicity attribution to either SBRT or ipilimumab will be described if possible.

Response: Clinical response at a non-index lesion will be scored using the immune-related response criteria (irRC) referred to as irRECIST 1.1 and discussed by others.(25,26) The index lesion will not be included in measuring response. The number of immune-related responses will be tabled by stratum and SBRT fraction dose level. **At the MTD**, the immune-related response rate and 95% exact CI will be estimated separately for previously untreated and previously treated metastatic patients and will inform our decision-making. The table below displays 95% exact CIs for selected numbers of responses.

95% Exact Confidence Interval for Event Rate based on 14 patients in each stratum at the Maximum Tolerated SBRT Fraction					
No. of Events	%	95% exact CI	No. of Events	%	95% exact CI
2	14.3	1.8 – 42.8	10	71.4	41.9 – 91.6
4	28.6	8.4 – 58.1	12	85.7	57.2 – 98.2
6	42.9	17.7 – 71.1	14	100.0	80.7*
8	57.1	28.9 – 82.3	* lower bound of 95% 1-sided CI		

Immune-related progression-free and overall survival will be estimated by the Kaplan-Meier method separately for previously untreated and previously treated metastatic patients who were treated at the MTD. The estimated 6 month irPFS and 12 month OS rates and 95% CIs will inform our decision-making, as they are considered by many to be better measures of clinical benefit. Interestingly, PFS6 and OS12 rates were approximately 25% and 45%, respectively, in 137 previously treated metastatic melanoma patients treated with ipilimumab alone.(3) Evaluation using historical benchmarks has been proposed by Korn et. al. for Phase II decision-making in metastatic melanoma (27).

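### Section 5.2 ends late-toxicity follow-up at progression, while 4.4.2 keeps following progressed patients for toxicity; the sections must be reconciled

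*Combined protocol and SAP*

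**What the plan says.** Section 5.2 leaves the late-toxicity window open-ended and notes that "late toxicities have been known to occur a year or more after therapy". It then closes the window: "Follow-up for late toxicity will cease when a patient experiences disease progression, since 2nd line therapies may then be initiated".

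Section 4.4.1 lists as its first ground for withdrawal "Progressive Disease as determined by irRECIST 1.1 criteria". For withdrawn subjects, 4.4.2 says: "Every effort will be made to follow subjects off study for toxicity, disease progression and survival".

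Three other places describe collection of later events, and none of them stops at progression:

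- Section 6.6 seeks records after the end-of-study visit, and permission to contact patients again about health and toxicity.
- Section 8.4.3 has events seen months after treatment recorded, and monitors both immune-related and SBRT-related ones.
- Section 9.2.1 continues reporting of attributable non-hematological Grade 3 events beyond 30 days. It also asks for notification of possibly related events at any time after a subject leaves the study.

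Late toxicity is a secondary objective (sections 2 and 8.2). Section 8.5 takes everyone who received any radiation or study medication into the toxicity analysis. It plans to grade and table late toxicities by stratum and dose level, and gives no method for time at risk or competing events.

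**The concern.** A site with a progressed patient cannot tell from the text whether to go on collecting late toxicity. The two readings give different data sets for the same secondary objective.

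If 5.2 is followed, observation ends at an event that is common in this disease and related to prognosis. Late-toxicity information then comes mainly from patients whose disease is controlled. A progressed patient who is alive but no longer observed would sit in an all-treated table as if free of late toxicity, so a proportion read from that table would tend to be too low.

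The reason given in 5.2, possible second-line therapy, concerns attribution. It is a reason to separate later events, not clearly a reason to stop collecting them. It is also tied to progression rather than to the actual start of new treatment. The DLT definition in 8.3 uses the latter trigger.

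**Working it through.** **Step 1: which instruction applies to a progressed patient.**

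| Section | Effect on a progressed patient |
|---|---|
| 4.4.1 | Withdrawn |
| 4.4.2 | Still followed for toxicity, as far as possible |
| 5.2 | Late-toxicity follow-up ends |
| 6.6, 8.4.3, 9.2.1 | Later events sought, recorded or reported; no stop at progression |

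Section 4.4.2 does not limit itself to acute toxicity, so it cannot be read as compatible with 5.2 without adding words.

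**Step 2: inputs for the size.** The documents contain no calculation of how many patients stay under late-toxicity follow-up, so there is no figure of the plan's own to reproduce. The relevant stated figures are:

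- Section 8.5: "PFS6 and OS12 rates were approximately 25% and 45%, respectively, in 137 previously treated metastatic melanoma patients treated with ipilimumab alone". These are cited external results and cannot be re-derived from the documents. Applying them here is an assumption.
- Section 3.1: "The protocol is designed for a maximum total of 40 patients".

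**Step 3: alive at 12 months.** 0.45 × 40 = 18. The other 40 − 18 = 22 have died and are lost under any follow-up rule.

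**Step 4: still under late-toxicity follow-up at 12 months if 5.2 governs.** These are the patients alive without progression.

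- Without extrapolation: PFS cannot rise after 6 months, so at most 0.25 × 40 = 10.
- Exponential PFS: S(12) = 0.25^(12/6) = 0.0625, and 0.0625 × 40 = 2.5.

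**Step 5: loss due to the rule alone (alive but no longer followed).**

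- Flat PFS after 6 months: 18 − 10 = 8, and 8/18 = 44% of survivors.
- Exponential PFS: 18 − 2.5 = 15.5, and 15.5/18 = 86% of survivors.

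Given the two benchmarks, 8 is a floor. The 15.5 is one plausible curve, not a ceiling.

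**Step 6: the same at 10.5 months**, the median time to severe toxicity that section 1.1 reports from a lung SBRT trial. With exponential OS, 0.45^(10.5/12) = 0.497, or 19.9 of 40 alive. Still followed: at most 10, or 0.25^(10.5/6) = 0.088, which is 3.5 of 40. Loss due to the rule: 9.9 to 16.4 of 19.9 (50% to 82%).

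**Step 7: sensitivity to the benchmark**, at 12 months with OS12 held at 45%.

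- PFS6 of 35%: at most 0.35 × 40 = 14 followed; exponential 0.35² = 0.1225, or 4.9. Loss: 4 to 13.1 of 18 (22% to 73%).
- PFS6 of 50%: exponential 0.50² = 0.25, or 10 followed. Loss: 8 of 18 (44%). The flat bound (20 of 40) exceeds the 18 alive, so it sets no useful floor.

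**The case against.** **Deaths are not losses due to the rule.** A reader might infer from 2.5 of 40 still followed that the rule removes most patients. It does not: about 22 of 40 would be dead by 12 months anyway, and the rule-only loss is 8 to 15.5 of 40 (20% to 39%). Even among survivors, whether it is a majority depends on the shape of the PFS curve. This objection stands, and the size is stated accordingly.

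**The benchmark may not transfer.** It is PFS rather than irPFS, for ipilimumab alone, in previously treated patients. This trial also enrols untreated patients and anticipates better efficacy. This stands as a limit on the size, not on the conflict between sections.

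**Event timing is not known.** A reader might infer that most late events could not be observed, because section 1.1 says "Severe toxicity occurred at a median of 10.5 months in 17% of those patients with peripheral lesions versus 46% with central lesions". That trial treated early-stage lung cancer at doses taken from a phase I study whose levels reached 20 to 22 Gy × 3, against 6 or 8 Gy × 3 here, and a median leaves about half of those events earlier. Section 5.2 says only that late events can occur at a year or beyond. The documents give no event-time distribution for this setting, so the inference fails. The 10.5 months is indicative only.

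**Other routes may capture the events.** Sections 6.6, 8.4.3 and 9.2.1 could still bring in late events after progression. It is therefore not shown that the data would be lost. This strengthens the case for reconciling the text.

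**Attribution after second-line therapy is a real problem.** Section 5.2 identifies SBRT toxicity by its place in the radiation portal and its consistency with radiation reaction, which might suggest that later events remain attributable. That helps only partly for in-field events. It does nothing for late immune-related events, which 8.4.3 also monitors.

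**No late-toxicity rate is specified.** Section 8.5 promises only tables, so the bias is conditional: it arises if the all-treated set is used as denominator.

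**Conclusion.** The conflict between 5.2 and sections 4.4.1 and 4.4.2 is certain from the text and needs to be resolved. If 5.2 governs, follow-up of a secondary safety objective ends informatively, and a table over all treated patients would tend to understate late toxicity.

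On the plan's benchmark figures, the rule alone takes about 8 to 15.5 of the 18 patients alive at 12 months out of late-toxicity follow-up (44% to 86%). This rests on PFS6 of about 25% and OS12 of about 45% holding in this population, and on a PFS curve between flat and exponential after 6 months. The direction is secure; the size is approximate. The documents support neither the claim that the rule by itself removes most patients nor the claim that most late events would go unseen.

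The change should be made, but the primary response and survival estimates are not affected.

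**What to change.** 1. Replace the stopping sentence in 5.2 so that late-toxicity data collection continues after progression, until death or last contact, on the same best-effort basis as 4.4.2 and 6.6.
2. Record the start date of any new systemic therapy. Table late events as before or after that date, the trigger that the DLT definition in 8.3 already uses. Show in-field SBRT-related and immune-related events separately.
3. In 8.5, report late toxicity with time at risk, for example as cumulative incidence with death as a competing event. Add a supportive analysis censored at the start of new therapy, which keeps the protection that 5.2 was seeking.

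This changes data collection and analysis only. The cost is somewhat more record retrieval from referring physicians, to whom patients return after the end-of-study visit, and one extra date per patient. Late grading from outside records will sometimes be incomplete. Some events after new therapy, especially immune-related ones, will have mixed attribution. With 20 patients per stratum the incidence estimates will be imprecise, so they should be presented as descriptive.
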